1.0 INVESTIGATORS

A list of Investigators is provided with the Investigator's Information and will be submitted to the FDA and IRB.

Statements of Qualifications:

Qualifications of investigators are provided in the Investigator Information and will be submitted to the FDA and IRB.

2.0 STATEMENT OF COMPLIANCE

This study will be conducted in accordance with any specific provisions of the associated Institutional Review Board(s) (IRBs) and 21 CFR Parts 812 and 312. This study will be conducted in accordance with the ethical principles that have their origin in the Declaration of Helsinki and that are consistent with Good Clinical Practice (GCP), ISO 14155 and the applicable national and regional regulatory requirements. Specifically, this study will be guided by the ethical principles of The Belmont Report, the Declaration of Helsinki, and the International Conference for Harmonization Good Clinical Practice (ICH-GCP).

4.0 LIST OF ABBREVIATIONS

AE	Adverse Event
AOM	Acute Otitis Media
CFR	Code of Federal Regulations
CRF	Case Report Form
CTA	Clinical Trial Agreement
dB	Decibels
DC	Direct Current
DIPS	Device Initiated Pause Sequence
EMLA	Eutectic Mixture of Lidocaine HCl and Prilocaine
ENT	Ear, Nose and Throat
FAS	Full Analysis Set
FDA	Food and Drug Administration
FPS-R	Faces Pain Scale- Revised
GCP	Good Clinical Practice
HCl	Hydrochloride
ICH	International Conference for Harmonization
IDE	Investigational Device Exemption
IFU	Instructions For Use
IND	Investigational New Drug Application
IO	In Office
IPS	Iontophoresis System
IRB	Institutional Review Board
ISO	International Organization for Standardization
LCD	Liquid-Crystal Display
MedRA	Medical Dictionary for Regulatory Activities
mITT	Modified Intent to Treat
MTT	Myringotomy with Tympanostomy Tube
NSR	Non-Significant Risk
OME	Otitis Media with Effusion
OR	Operating Room
PSA	Pressure-Sensitive Adhesive
SAE	Serious Adverse Event
SD	Standard Deviation
TDS	Tube Delivery System
TM	Tympanic Membrane
TT	Tympanostomy Tube
UADE	Unanticipated Adverse Device Effect
VAS	Visual Analogue Scale

5.0 PROTOCOL SUMMARY

Brief Title:	ADEPT; ADult study to Evaluate Placement of tympanostomy Tubes in-office
Working Title:	A prospective, multicenter study to evaluate effectiveness and safety of lidocaine iontophoresis and tympanostomy tube placement using the TULA iontophoresis and tube delivery systems for adults in an office setting.
IDE Protocol	IDE GI170002
Sites / Enrollment	Up to 11 investigational sites (2 Group A, up to 9 Group B) Up to 85 enrolled subjects to yield 70 evaluable subjects (40 Group A, 30 Group B).
Brief Summary:	
The objectives of this study are two-fold:
 
 1) to determine if active lidocaine iontophoresis is superior to sham lidocaine iontophoresis in providing anesthesia to the tympanic membrane, and 2) to evaluate tolerability and safety of tympanostomy tube (TT) placement in adults following local anesthesia in a physician’s clinic setting (henceforth referred to as ‘in-office’). 
This study will consist of two independent Groups, hereafter referred to as Group A and Group B. Each group has its own primary endpoint, both of which must pass the statistical test for the overall study to be considered successful and to meet the study objectives. In addition, safety will be evaluated by review of the occurrence of adverse events.
 
The IPS will be used to facilitate anesthetic delivery to the tympanic membrane (TM). The Iontophoresis System consists of an Iontophoresis Control Unit, Iontophoresis Earsets and a return electrode patch. The Control Unit monitors and delivers a fixed amount of charge (ie, dose) to the patient through the Earsets(s) and alerts the operator when charge delivery is complete. [REDACTED]
 
[REDACTED]
 
[REDACTED]
 
[REDACTED]
 
[REDACTED]
 
[REDACTED]
 
[REDACTED]
 
[REDACTED]
 
[REDACTED]
 
[REDACTED]
 
[REDACTED]
 
[REDACTED]
 
[REDACTED]

The lidocaine-based solution used for local anesthesia of the TM is 2% lidocaine HCl/ 1:100,000 epinephrine, an FDA-approved drug commercially available for other indications but is not indicated for topical administration to the TM, nor for iontophoretic administration. Therefore, the drug used in this study is considered an investigational drug for the purposes of the study. [REDACTED]

The TDS is a mechanical device that integrates a myringotomy blade, tympanostomy tube and tube inserter for TT placement with a user-controlled activation. [REDACTED]

This study will consist of two independent Groups, hereafter referred to as Group A and Group B. Each group has its own primary endpoint, both of which must pass the statistical test for the overall study to be considered successful.

Group A will consist of 40 evaluable healthy adult subjects aged 18-50 years (inclusive), enrolled at two investigational centers in the US.ⁱ Otologic examination, cranial nerve physical exam, tympanometry and audiometry will be conducted at the screening visit.

Group A subjects will be randomized (1:1) to receive unilateral treatment (1 ear) with either active lidocaine iontophoresis or sham lidocaine iontophoresis. The sham iontophoresis procedure will be identical to the active lidocaine iontophoresis, with the exception that the iontophoresis current will not be activated (ie, the same drug solution will be applied to ears in both arms). After the completion of the iontophoresis procedure, the tympanic membrane will be tapped with a dull otologic probe to test the level of anesthesia. The subject will rate the level of pain using the Visual Analogue Scale (VAS) immediately after the tap. The Investigator will also assess the level of anesthesia whether adequate for a hypothetical tube placement. Investigators and subjects will be blinded to treatment assignment. A follow-up at 3 days is required for all subjects, at which point otologic examination, cranial nerve exam, tympanometry and

ⁱ Subjects who are consented for the study will be considered enrolled. Throughout the protocol, enrollment numbers will reflect consented enrolled subjects with evaluable data. Enrolled subjects who are determined to be ineligible (screening failures), who withdraw prior to the study procedure or who are replaced are not included in the enrollment subject counts presented herein. Further definition of subjects included in the analysis sets is provided in Section 14- Statistical Methods

[figure not shown]
audiometry will be conducted. If there are unresolved device, procedure or drug-related adverse events at the 3-day follow-up visit, a 12-day follow-up visit is required.

Group B will consist of 30 evaluable adults age 18 years or greater who require unilateral or bilateral tube insertion enrolled at up to 9 centers in the US. Otologic examination, cranial nerve physical exam, tympanometry and audiometry will be conducted at the screening visit.

Group B subjects will receive active lidocaine iontophoresis and will have tubes placed using the TDS in all ears indicated for tube placement. The subject will rate the pain upon TDS tube insertion using the VAS, and the pain score will be compared to a performance goal. [REDACTED]

[REDACTED]
[REDACTED]
[REDACTED]
[REDACTED] Vital signs (diastolic and systolic blood pressure, heart rate, respiratory rate and pulse oximetry) will be monitored prior to and periodically up to 1 hour following iontophoresis. A follow-up at 3 weeks is required for all subjects, at which point otologic examination, cranial nerve physical exam, tympanometry and audiometry will be conducted.

Study Design:	Study Phase: Pre-Pivotal
	Group A: No. of Centers: 2 Number of Arms: Randomized (1:1), double-blind, sham-controlled design with two arms (active lidocaine iontophoresis vs sham lidocaine iontophoresis) Enrollment: 40 healthy adult subjects
	Group B: No. of Centers: up to 9 Number of Arms: Single arm Enrollment: 30 adult subjects requiring tympanostomy tubes
Safety Evaluations	Safety Evaluation will include the following assessments: 
 • Otoloscopic examination for visual inspection of external ear canal and TM condition at baseline, post-procedure and at the follow-up visit(s). The post-procedure exam also includes an examination of the myringotomy wound and tympanostomy tube for Group B subjects. • Audiometry to assess hearing at baseline and at the follow-up visit(s). • Tympanometry to assess tympanic membrane, middle ear conditions and tube function (Group B only) at baseline and at the follow-up visit(s). • Cranial nerve physical exam to assess cranial nerve function at baseline, post-procedure (Group B only) and at the follow-up visit(s). • Vital signs (blood pressure, oxygen saturation, respiratory and heart rates) prior to and up to one-hour following iontophoresis (Group B only). • Adverse events
Endpoints:	Primary Endpoints: Group A 
 • Anesthesia Effectiveness: Subject-reported pain score elicited by tympanic membrane tap following active lidocaine iontophoresis compared to sham lidocaine iontophoresis using the VAS. Group B 
 • Tube Placement Tolerability: Subject-reported pain score following TDS tube placement using the VAS by subject compared to a performance goal.
	Secondary Endpoints: None
	Safety Endpoint: 
 • Safety: Occurrence of adverse events, by subject (both Groups A and B)

	
Eligibility Criteria:	
Inclusion Criteria:
 
Group A: At least one ear must meet ear-specific eligibility criteria. Group B: Each ear indicated for tube placement must meet ear-specific eligibility criteria.
 
Group A:
 
1. Healthy adults, 18-50 years old at time of consent2. Subject is able and willing to comply with the protocol and attend all study visits3. Subject is able and willing to provide informed consent4. Subjects with air conduction hearing thresholds of 25 dB HL or better at standard frequencies up to 2000 Hz, and 45 dB or better at 4000 Hz.5. Subject is able to read and understand English

	
Group B:
 
 1. Adults at least 18 years of age at time of consent 2. Indication for tympanostomy tube insertion per Clinical Practice Guideline,¹ or indicated for tympanostomy tube insertion tube insertion due to barotrauma or Eustachian tube dysfunction per AAO-HNS Clinical Indicators.² 3. Subject is able and willing to comply with the protocol and attend all study visits. 4. Subject is able and willing to provide informed consent. 5. Subject is able to read and understand English. <hr/> 
Exclusion Criteria:
 
Group A:
 
 1. Pregnant or lactating females. 2. Prior ear iontophoresis procedure experience. 3. Subjects with conductive hearing loss. 4. Subjects with history of sensitivity or allergic reaction to lidocaine HCl, tetracaine, epinephrine, or any hypersensitivity to local anesthetics of the amide type, or any component* of the anesthetic drug formulation. 
*Subjects with a known hypersensitivity to methylparaben and/or propylparaben (preservatives used in lidocaine HCl formulations), or to their metabolite para amino benzoic acid (PABA), or other components including potassium metabisulfite, sodium metabisulfite, ededate disodium or citric acid.
 
 5. Familial history of insensitivity to lidocaine or other local anesthetics of the amide type. 6. Significantly atrophic, retracted, bimeric, monomeric or atelectatic tympanic membrane. 7. Perforated tympanic membrane. 8. Subjects with known history of ear surgery or TM condition that has the potential to affect the sensitivity of the TM (eg, prior tympanostomy tube insertion). 9. Otitis externa. 10. Damaged/denuded skin in the auditory canal. 11. Subjects with electrically sensitive support systems (eg, pacemakers, defibrillators, cochlear implants). 12. Cerumen impaction resulting in a significant amount of cleaning required to visualize the tympanic membrane. 13. Evidence of Otitis Media at day of procedure, or within the past three (3) months prior to procedure. 14. Other conditions that would preclude performing the study procedure including ear plug incompatibility.
--	-----------------------------------------------------------------------------------------------------------------------------------------------------------------------------------------------------------------------------------------------------------------------------------------------------------------------------------------------------------------------------------------------------------------------------------------------------------------------------------------------------------------------------------------------------------------------------------------------------------------------------------------------------------------------------------------------------------------------------------------------------------------------------------------------------------------------------------------------------------------------------------------------------------------------------------------------------------------------------------------------------------------------------------------------------------------------------------------------------------------------------------------------------------------------------------------------------------------------------------------------------------------------------------------------------------------------------------------------------------------------------------------------------------------------------------------------------------------------------------------------------------------------------------------------------------------------------------------------------------------------------------------------------------------------------------------------------------------------------------------------------------------------------------------------------------------------------------------------------------------------------------------------------------------------------------------------------------------------------------------------------------------------------------------------------------------------------------------------------------------------------------------------------------------------------------------------------------------------------------------------------------------------------------------------------------------------------------------------------------------------------------------------------------------------------------------------------------------------------------------

	
15. Health conditions that, in the opinion of the investigator, would present undue risk to the subject, based on device/anesthetic drug product label warnings and precautions.
 
Group B Ear-Specific Exclusion Criteria
 
 1. Significantly atrophic, retracted or retraction pocket at location of tube placement, bimeric, monomeric or atelectatic tympanic membrane. 2. Perforated tympanic membrane. 3. Otitis externa. 4. Hemotympanum. 5. Damaged/denuded skin in the auditory canal. 6. Cerumen impaction resulting in a significant amount of cleaning required to visualize the tympanic membrane potentially causing abrasion or irritation to the external ear canal. 7. Notable ear discomfort experienced during audiologic or otoscopic examination. 8. Anatomy that precludes sufficient visualization of and access to the tympanic membrane. 9. Anatomy that necessitates tympanostomy tube placement in the posterior half of the tympanic membrane. 
Group B General Exclusion Criteria
 
 10. Pregnant or lactating females 11. History of sensitivity or allergic reaction to lidocaine HCl, tetracaine, epinephrine, or any hypersensitivity to local anesthetics of the amide type, or any component* of the anesthetic drug formulation. 
*Subjects with a known hypersensitivity to methylparaben and/or propylparaben (preservatives used in lidocaine HCl formulations), or to their metabolite para amino benzoic acid (PABA), or other components including potassium metabisulfite, sodium metabisulfite, ededate disodium or citric acid.
 
 12. Familial history of insensitivity to lidocaine or other local anesthetics of the amide type. 13. Electrically sensitive medical support systems (eg, pacemakers, defibrillators, cochlear implants) 14. Other conditions that would preclude performing the study procedure including iontophoresis system ear plug incompatibility. 15. Health conditions that, in the opinion of the investigator, would present undue risk to the subject, based on device/anesthetic drug product label warnings and precautions.

Sample Size and Power	
Group A:
 
A sample size of 40 subjects will provide greater than 95% power at the one-sided 2.5% significance level for a permutation test on the difference in mean VAS scores between the two arms. The null and alternative hypotheses are:
 $H_0: \mu_T - \mu_S = 0$ $H_1: \mu_T - \mu_S < 0$ 
Group B:
 
A sample size of 30 subjects will provide greater than 95% power at the one-sided 2.5% significance level for a bootstrap test of the mean VAS score against a performance goal of 4.5. The null and alternative hypotheses are:
 $H_0: \mu \geq 4.5$ $H_1: \mu < 4.5$
------------------------------	------------------------------------------------------------------------------------------------------------------------------------------------------------------------------------------------------------------------------------------------------------------------------------------------------------------------------------------------------------------------------------------------------------------------------------------------------------------------------------------------------------------------------------------------------------------------------------------------------------

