12.2.3. Cranial Nerve Physical Exam

A standard cranial nerve physical exam will be employed at screening, post-procedure and at the follow-up visit to identify any potential adverse effects. [REDACTED]

[REDACTED]

[REDACTED] Any abnormalities will be recorded at screening and at the follow-up visit and the subject will be assessed for any adverse events. [REDACTED]

[REDACTED]

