12.5. Procedure

12.5.1. Vital Signs (Group B)

Vital signs (diastolic and systolic blood pressure, heart rate, respiratory rate and pulse oximetry) will be monitored 15 minutes and immediately prior to iontophoresis, and again immediately following iontophoresis, following tube placement, 30 minutes and 60 minutes after completion of iontophoresis for all Group B subjects.

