12.5.10. Tympanostomy Tube Placement (Group B only)

In at least one ear, the Investigator will place the TT using the TDS while the subject’s head is gently stabilized by the clinic staff, as is typical for standard of care ear examinations. If the TT is not successfully placed by the TDS device, the investigator may choose to attempt tube placement with another TDS device. [REDACTED]

Following TDS tube placement, the subject will report their post-tube placement ear discomfort for each ear undergoing tube placement using the VAS. For bilateral tube placement subjects, the ‘worst’ ear pain score (highest score) will be used for analysis of the tube placement tolerability primary endpoint. [REDACTED]

[REDACTED] The subject’s VAS score for each ear following suction will be recorded. Post-operative care, including otic drops, will be prescribed per investigator’s discretion. All post-operative medications will be documented.

If an unexpected serious complication occurs during the procedure, the procedure will be terminated. The Investigator will take all appropriate intra- and post-treatment measures to ensure subject safety and proper treatment. The Investigator will notify Tusker Medical and their IRB immediately, but in no instances greater than 24 hours of the incident.

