12.5.11. Cranial Nerve Exam

The cranial nerve physical exam will be conducted post-procedure.

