12.8. Summary- Study Evaluations, Group A

The schedule of evaluations for each study visit for Group A is presented in **Table 2**.

Table 2. Schedule of Evaluations – Group A

Evaluation	Screening	Procedure	3 Days (-1 /+2 days)	12 Days * (±3 days)
Informed Consent	✓			
Medical History	✓			
Cranial Nerve Physical Exam	✓	✓	✓	✓
Inclusion/ Exclusion Criteria	✓	✓ (verification)		
Concomitant Medications	✓	✓	✓	✓
Otoscopy	✓	✓	✓	✓
Tympanometry	✓ (within 28 days prior to Procedure)		✓	✓
Audiometry	✓ (within 28 days prior to Procedure)		✓	✓
Randomization	✓			
Iontophoresis/Sham Iontophoresis		✓		
Anesthesia Effectiveness		✓		
Adverse Events		✓	✓	✓
Study Exit			✓ (if no 12 day visit required)	✓

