14.7 Cranial Nerve Function

Cranial nerve function physical examination will be performed for all subjects at screening, post-procedure and at all follow-up visits. The change from baseline for subjects in the Safety Analysis set in each Group will be presented for all follow-up visits.

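### The protocol summary limits the post-procedure cranial nerve exam to Group B while Table 2 and SAP 14.7 include Group A; SAP 14.7 then plans no summary of that exam and shows no active/sham split

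*Protocol*

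**What the plan says.** **Who is examined after the procedure.** The Safety Evaluations entry in protocol section 5.0 lists the "Cranial nerve physical exam to assess cranial nerve function at baseline, post-procedure (Group B only) and at the follow-up visit(s"), which excludes Group A on the procedure day. Table 2 (section 12.8), the Group A schedule, has a row "Cranial Nerve Physical Exam" ticked at Screening, Procedure, 3 Days and 12 Days. Section 12.5.11 states, without naming a group: "The cranial nerve physical exam will be conducted post-procedure". Section 12.2.3 says: "A standard cranial nerve physical exam will be employed at screening, post-procedure and at the follow-up visit to identify any potential adverse effects"; some text after that sentence is redacted. SAP 14.7 is explicit: "Cranial nerve function physical examination will be performed for all subjects at screening, post-procedure and at all follow-up visits".

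**What is recorded and summarised.** The visible text of 12.2.3 goes on to plan the recording of abnormalities at screening and at follow-up, and does not name the post-procedure exam. SAP 14.7 sets the summary: "The change from baseline for subjects in the Safety Analysis set in each Group will be presented for all follow-up visits".

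**How neighbouring assessments are handled.** SAP 14.4 (audiometry) and 14.5 (tympanometry) both call for results by active and sham arm in Group A. SAP 14.6 (otoscopy) has the same form as 14.7: by Group, at screening and follow-up only. SAP 14.2 and 14.3 do summarise procedure-day measurements, namely vital signs and return-electrode erythema.

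**The concern.** Two separate things look wrong.

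The first is a scheduling contradiction. Sites working from the summary and sites working from Table 2 would treat Group A differently on the procedure day. Group A consists of healthy volunteers, for whom protocol section 10.0 acknowledges no benefit, so a scheduled safety exam should not depend on which page a site reads.

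The second is a reporting gap. The exam closest to exposure is the one most likely to catch a transient effect of drug or current on a cranial nerve. SAP 14.7 schedules that exam and then leaves it out of the only planned table. In Group A the table as described also shows no separation of active from sham, although that is the study's randomized comparison. A short-lived difference between arms, too minor to be called an adverse event, would appear in no table. Such a difference would reflect current together with the drug uptake it drives, not current alone, because both arms receive the same solution.

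**Working it through.** The plan states no figure on this point. The check is a comparison of texts, followed by simple counts.

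**Step 1: which version governs Group A.**
- Against Group A: section 5.0 only.
- For Group A: Table 2 and SAP 14.7 expressly; 12.5.11 and the visible text of 12.2.3 by setting no group limit.
- The Procedure tick in Table 2 does not itself say before or after treatment. Sections 12.2.3 and 12.5.11 and SAP 14.7 all place the procedure-day exam after it.
- Group-specific steps elsewhere in section 12.5 carry the group in the heading: 12.5.1, 12.5.8, 12.5.9 and 12.5.10 (for example "12.5.10. Tympanostomy Tube Placement (Group B only"). The heading of 12.5.11 carries none.

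The body of the protocol therefore most likely intends both Groups, and the summary is the outlier.

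**Step 2: what the SAP 14.7 table covers.** The exam-times sentence names post-procedure separately from follow-up visits. The summary sentence then names follow-up visits only. Sections 12.6 and 12.7 define follow-up as day 3 (with a conditional day 12) in Group A and week 3 in Group B. The procedure day is not a follow-up visit, so its exam falls outside the table in both Groups.

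**Step 3: how many exams are left out.** Inputs are 40 evaluable subjects in Group A and 30 in Group B (sections 5.0 and 11.2), and the visits in Tables 2 and 3. The conditional 12-day visit is not counted.
- If Table 2 governs: Group A 40 × 2 = 80, Group B 30 × 2 = 60, total 140. Procedure-day exams: 40 + 30 = 70. Share not summarised: 70/140 = 50%.
- If the summary governs: Group A 40 × 1 = 40, Group B 30 × 2 = 60, total 100. Procedure-day exams: 30. Share not summarised: 30/100 = 30%.
- Difference between the two versions: 70 − 30 = 40 procedure-day exams, all in Group A.

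**Step 4: the earliest exam that reaches the table.** Visit windows come from sections 12.6 and 12.7.
- Group A: 3 − 1 = day 2 to 3 + 2 = day 5.
- Group B: 21 − 7 = day 14 to 21 + 7 = day 28.

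**Step 5: the arm split.** The SAP uses Group to mean A or B (sections 5.0 and 14.1). SAP 14.4 and 14.5 add the Group A arms in so many words and 14.7 does not. With 1:1 allocation the arms are 40/2 = 20 each, so on the visible wording the Group A result would be shown for 40 subjects, not for 20 and 20.

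**The case against.** The contradiction is one parenthesis in a summary, and all the visible operative text points the other way, so the practical risk at sites is small. That is fair, but the correction is still needed.

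On reporting, the other side has more to say. The safety endpoint is occurrence of adverse events. Protocol 13.1 turns any clinically significant change found at a protocol evaluation into an adverse event. Those events are tabulated by treatment (protocol 14.3.4, SAP 14.1) and reported for the procedure visit (SAP 14.1). SAP 22.0 lists all case report form data per subject with the Group A treatment, SAP 24.0 shows blank fields as blank, and SAP 17.0 summarises missing data. SAP 14.7 also follows the visible recording sentence in 12.2.3, and otoscopy is handled the same way, which suggests a convention and not an oversight. All of this stands and limits the point to findings below adverse event level. The recording sentence has a second consequence: the visible text does not assure that minor procedure-day findings are captured at all, so the listings may not be a full fallback. Redacted text nearby may settle this.

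A reader might infer more than the documents support:
- **That active and sham are definitely pooled.** SAP 14.7 shows no split but does not say the arms are combined. Protocol 14.2 (General Statistical Methods) is redacted, and a general by-arm rule there cannot be excluded.
- **That the randomized safety comparison is lost.** Adverse events, audiometry and tympanometry are all reported by arm.
- **That under the summary Group A gets no immediate safety check.** Post-procedure otoscopy and procedure-visit adverse event assessment apply either way; only the cranial nerve component is in question.
- **That half of the exams go unreported.** The 50% figure assumes Table 2 governs, and it counts exams missing from a summary table, not exams missing from the report.

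**Conclusion.** Both parts hold, and both are minor. The scheduling contradiction is certain on the text: 40 procedure-day exams in Group A are required by Table 2 and SAP 14.7 and excluded by the summary. The absence of a planned summary for the procedure-day exam is also clear from SAP 14.7, and amounts to 30% to 50% of scheduled post-baseline exams depending on which schedule governs. The lack of an active/sham split is what the visible text shows, subject to the redaction of protocol 14.2.

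The counts use the planned evaluable numbers and leave out the conditional 12-day visit; they measure coverage of a table, not risk to subjects. Primary endpoints, sample size and the adverse event endpoint are unaffected.

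**What to change.** 1. In protocol section 5.0, delete the parenthetical restriction to Group B from the cranial nerve entry. If the restriction was intended, correct Table 2, 12.2.3, 12.5.11 and SAP 14.7 instead.
2. In protocol 12.2.3, add post-procedure to the sentence on recording abnormalities, and confirm that the case report form captures the result.
3. In SAP 14.7, add the post-procedure time point to the change-from-baseline summary, with the number examined, by Group and by active and sham arm in Group A.

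The cost is a few words in the protocol, one table row and one column split, and possibly a small case report form change if procedure-day results are not already collected. No exam is added beyond those in Tables 2 and 3. Whether otoscopy (SAP 14.6) should get the same treatment can be decided at the same time.
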